## **SCOR P1 and MJ**

### **Rules/Changes**

**Last Updated: 9/8/16**

- In order to be eligible at BL, subject must be averaging 4.5 CPD for the past 2 weeks. If a subject is smoking less than 4.5 CPD, they will be dropped from the study and filed as "SCREEN FAIL" (1/1/15).
- Week 0 clinic visit must be completed on the subject's quit date. If this is not possible, it may be completed AFTER the quit date but a protocol deviation must be made. Week 0 cannot be completed BEFORE quit date (1/3/15).
- Subjects are allowed to miss 2 clinic visits over the entire study to eligible for the \$75 bonus at Week 12 – unless a cancellation was made by study staff (instead of the subject). That absence would NOT count against the bonus (1/29/15).
- ALT/AST levels must not be higher than double the normal range to be enrolled at SC. If levels are higher than double the normal range, the subject will be notified of the results, referred to PCP for follow-up and invited back in 4 weeks to re-test. If levels are high but within double the normal range, the subject may be enrolled per [name] approval. He/she will be tested again at Week 1 and as long as levels have not gone up, they will be allowed to continue in the study (1/29/15).
- The last available time to start a follow-up appointment will be 5:00pm (Week 4, 8, 12 – 4:30pm)
- We will only collect 2 urine samples at each visit (00 & 01) (4/7/15).
- Samples to be sent for analysis:

Hormones	BL	W4	W12	(Blood)
Cotinine		W4	W12	(Blood)
- BDI scores will be monitored weekly by study staff. If a subject scores  $\geq 20$  or endorsed suicidal thoughts (Question #9), staff will start an AE and continue to monitor scores. If score decreases and is  $< 14$  after three weeks with no suicidal thoughts, the AE may be closed.

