**Inclusion Criteria:** • Male 18 to 60 years old or female between 18 and 50 years old; • Self-report smoking ≥ 5 cigarettes/day for at least the past year; • Motivated to quit smoking (self-report ≥ 7 on 10-point Likert-type scale); • In stable physical/mental health; • Self report of regular menstrual cycles (female only) • Willing to use double-barrier contraception method if sexually active and not surgically sterilized; • English fluency; • Understand the study procedures and able to provide informed consent; • Ability to participate fully in research elements for the duration of the trial.

**Exclusion criteria:** • Current use of other types of tobacco, nicotine replacement therapy, or smoking cessation medications; • Current or recent (< 3 months) breastfeeding (females only); • Current or planned pregnancy within the next three months (females only); • DSM-IV diagnoses for psychotic disorders, bipolar disorder, ADHD, major depressive disorder within the last 3 months, • Substance dependence within the last 3 months with the exceptions of nicotine dependence and non-daily use of marijuana.; • Unstable psychotropic medications (< 3 months); • Current use of exogenous hormones, finasteride (propecia), efavirenz, red clover, ketoconazole and other drugs that are CYP3A4 inhibitors; • Conditions contraindicated to progesterone treatment (including, but not limited to, thrombophlebitis, deep vein thrombosis, pulmonary embolus, clotting or bleeding disorders, heart disease, diabetes, history of stroke, allergy to peanuts, hypersensitive to progesterone and liver dysfunction).

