#### **B.4.3. Visit Sequence & Procedures**

**Screening Visits (Visits 1 and 2):** Initial screening procedures for Project I and II will be identical except for drug use related criteria, testing and evaluation. Candidates completing the consent process will be screened in a two-visit process. For males, this two-visit process will be scheduled within two weeks of completion of the phone interview. For females, this two-visit process will be completed during the follicular phase of their menstrual cycle to avoid any potential menstrual phase effects on smoking behavior or mood measures, as well as to limit wait time for initial study procedures (details below). Therefore, after the phone screen females will be told to call with the first day of their next period, and then the two-part screening visits will be scheduled during days 1-7 (where Day 1 is the onset of menses) of the menstrual cycle. We have used this procedure with success in our ongoing trial on menstrual phase and depressive symptoms.

At the first of two screening visits (Screening Visit 1), the study will be described in detail to candidates by the study coordinator, and informed consent will be obtained. Subjects agreeing to participate will undergo medical, psychiatric and other evaluation to determine eligibility. The medical evaluation will include: brief physical exam (height, weight, blood pressure, heart rate, and medical history interview), audiotaped psychiatric interview, carbon monoxide level and a blood draw (for measurement of serum hormone levels and liver function via ALT and AST measurement) and a urine pregnancy test (females only). Trained staff will conduct all interviews including the Structured Clinical Interview for DSM-IV (SCID; First, 1995) and instrument administration with audiotapes reviewed regularly to sustain fidelity. Self-report instruments measuring

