Since this entails a delay of variable duration from Screening Visit 2 to Baseline

Visit (thus impacting timing of medication initiation) across female subjects, each *male subject* will be matched to a female subject for a similar delay so that, across the male and female groups, study procedures will be follow a similar chronology.

**Baseline Visit (Visit 3):** When the LH surge occurs female subjects will be instructed to come into the clinic within three days for their baseline visit and to start medication. Male subjects will be instructed to come into the clinic according to their assigned delay (per list generated by the Biostatistics Core). This visit will occur seven days prior to quit date. At this visit, subjects will be randomized to PRO or PBO within strata defined by sex. The Statistical Analysis Core (SAC) will generate the randomization tables (one for each sex), and the Clinical Trials Research Pharmacy will use it to determine randomization assignment. Randomization assignment will be stored in a secure file in a secure location at the Clinical Trials Research Pharmacy, to be shared only with the SAC. All other project staff including PI and study coordinator, as well as the participant, will remain blinded to the randomization assignment.

At the baseline visit subjects will provide a blood sample (for hormone assessment), breath sample (to confirm smoking status via carbon monoxide breathalyzer), have their vital signs (blood pressure, heart rate, weight) measured, be informed of their quit date, and receive brief behavioral counseling to prepare for their quit date. At the end of this visit subjects will be paid for their time and given study medication along with instructions for taking the medication (beginning at 8PM that day), as well as a clinic visit schedule for the remaining clinic visits. This visit will take approximately one hour to complete.

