Study Adherence: To encourage compliance the following will occur: (1) at the Baseline Visit, subjects will be given a schedule of all remaining appointments; (2) at each visit the subjects will be given an appointment reminder card for the next visit; (3) reminder calls, texts and/or emails (per subject's preference) will be placed or sent the day before each visit; (4) subjects will be routinely reminded that regardless of their smoking status their data are valuable and important; and (5) regardless of smoking status, subjects will be compensated at each visit (described in the following). If a subject misses a visit, study staff will try to reach him/her by phone that day to reschedule for one to three days later. If that does not work, staff will contact the subject's designated 'contact person' (i.e., someone who does not live with the subject but knows how to get in touch). If a subject does not attend any visits after the screening visits, he/she will be labeled as a "drop" and replaced. If the subject discontinues from the study after randomization but before the final follow-up visit, he/she will be labeled an "*incomplete*" but not replaced. If a subject does not quit on their assigned quit date or relapses later, she/he will be encouraged to stay in the study and make another quit attempt; such that we will follow them for three months regardless of smoking status. Subjects who complete the four week follow-up period after quit date, regardless of smoking status, will be labeled a "*completer*" for the primary outcome and not replaced. Our sample size goal to sufficiently power the primary outcome is for 200 completers.

[figure not shown]

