#### B.4.8. Statistical Analysis

Randomization scheme: Our power calculation for the primary outcome specifies 100 males and 100 females. Since we expect approximately 25% drop-out before determination of the primary endpoint, we will over-enroll, approximately 125 of each sex. Thus we will build randomization tables for up to 150 male and 150 female potential enrollees. Each sex group will be randomized 1:1 to PRO vs. PBO. Since enrollment and randomization will occur over several years, we will employ a randomly permuted blocks allocation, rather than a simple random allocation, stratified by sex. This will reduce the possibility of a chance imbalance in treatment assignments, ensuring that we have treatment balance maintained within sex group consistently across the enrollment period. Block sizes of 4 and 6 will be used in a 1:1 ratio.

Primary outcome analyses: This addresses Hypothesis 1. Our primary outcome is the binary indicator of relapsed yes/no at the week 4 visit. An unadjusted assessment of the treatment effect will come from a logistic regression of this binary outcome on randomized treatment assignment, separately by sex. The sex-specific treatment effect will be considered statistically significant if the p-value is <0.025. All persons randomized and with a measured primary outcome at the week 4 visit will be included in this analysis, regardless of whether or not they ever took any of their assigned treatment (intent-to-treat analysis); persons with missed visits are discussed below. While we expect baseline covariates to be balanced across treatment groups due to the randomization, an adjusted assessment of the treatment effect will then be carried out by a logistic regression including the randomized treatment assignment and pre-specified adjusting covariates such as age, baseline progesterone, estradiol, baseline impulsivity measures, etc. This pre-specified list will be determined by the study team during the finalization of the protocol, prior to the first study enrollment. We expect these analyses to be somewhat conservative, since they do not explicitly account for the randomized permuted blocking (Matts and Lachin, 1988). An analysis that accounts for the blocking (such as a stratified Mantel-Haenzel test) cannot be generalized to include the adjustment for impulsivity measures, for example, which are a focus of this proposal.

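### Participants enrolled with mildly raised ALT/AST may leave the study on a Week 1 result taken 14 days after randomisation, with no provision to keep collecting their outcome

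*Combined protocol and SAP*

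**What the plan says.** - **Who is retested.** B.4.3 schedules "liver function via ALT and AST measurement" at Screening Visit 1. The operating rules then deal with raised results: "If levels are high but within double the normal range, the subject may be enrolled", subject to approval. A condition is attached: "He/she will be tested again at Week 1 and as long as levels have not gone up, they will be allowed to continue in the" trial. No other Week 1 liver test appears in the documents.
- **When randomisation happens.** B.4.3, Baseline Visit: "At this visit, subjects will be randomized to PRO or PBO within strata defined by sex". Study drug starts that evening. The quit date (Week 0) is seven days later, and visits are weekly after that (Table 1).
- **Who is analysed.** B.4.8 takes randomised persons who have a measured Week 4 outcome, "regardless of whether or not they ever took any of their assigned treatment (intent-to-treat analysis".
- **What happens to leavers.** B.4.3, Study Adherence: "If the subject discontinues from the study after randomization but before the final follow-up visit", the person is labelled *incomplete* and is not replaced.
- **Missing Week 4 outcomes.** B.4.8 makes three runs: without these persons, with a self-reported recall collected in Week 5 by phone or email, and with all of them taken as relapsed. It also compares those missing and not missing Week 4 on baseline characteristics and treatment assignment.
- **Eligibility.** The exclusion lists in B.4.2 and in the Data Safety and Monitoring Plan include "history of stroke, allergy to peanuts, hypersensitive to progesterone and liver dysfunction", with no enzyme threshold.

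**The concern.** The rule makes remaining in the trial depend on something measured after randomisation and after two weeks on assigned treatment. Its wording is about the study and not the medication. Elsewhere the documents keep the two apart: intolerance leads to a dose change (B.4.5), and suspected thrombosis to stopping study medication (DSMP section F). Staff who follow the liver rule literally would end the visits as well.

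Two things are at stake. If progesterone has any effect on the enzymes, removal will differ between the arms, and the Week 4 comparison is then made in a group selected on a treatment-affected result. If it has none, randomised participants are lost to ordinary variation between two blood draws, because the condition has no margin: any rise counts.

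**Working it through.** **1. Timing.** Baseline, randomisation and first dose = day 0. Week 0 = 0 + 7 = day 7. Week 1 = 7 + 7 = day 14. Week 4 = 7 + 28 = day 35. The retest therefore follows 14 days of assigned treatment and precedes the primary outcome by 35 − 14 = 21 days.

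**2. What follows for a removed participant.** No Week 4 visit means no measured outcome, so the person is outside the main analysis set in B.4.8. Study Adherence gives no replacement. The three-month follow-up promised there is tied to smoking status and does not mention safety stops. What remains is Week 5 recall, which has no CO or cotinine confirmation, or being counted as relapsed.

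**3. The plan's power figure, to show that power is not the issue.** Inputs from B.4.7: placebo relapse 66%, odds ratio 3.5, 50 per arm within each sex, two-sided alpha 0.025. PRO odds = (0.66/0.34)/3.5 = 0.555, so PRO relapse = 0.555/1.555 = 35.7%. Pooled-variance chi-square power is 79.7%, which reproduces the stated 80%. If 1 to 5 participants per sex are lost (assumption), power is 79.2–77.2% when all are PRO, and 78.8–74.8% when each arm loses that many.

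**4. How far selection could move the estimate.** Assume no true effect, so 33 of 50 relapse in each arm, and remove *k* = 1 to 5 PRO participants. The odds ratio is PBO over PRO; above 1 favours PRO.
- All removed would have relapsed, measured outcomes only: (33/17) / ((33 − *k*)/17) = 1.03 to 1.18.
- All removed would have been abstinent but are counted as relapsed: (33/17) / ((33 + *k*)/(17 − *k*)) = 0.91 to 0.61.

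These are deliberate extremes. They show that the two runs can err in opposite directions.

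**5. How often an unchanged liver test would show a rise.** The documents give no inputs, so all of these are assumptions: log enzyme = true level + error; between-person log SD 0.4; within-person CV 10, 20 or 30%, with error SD = √ln(1 + CV²); upper limit set so that 5–15% of single values exceed it; screening value between 1 and 2 times that limit; true level unchanged at Week 1. Simulation with 2,000,000 people:

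| | CV 10% | CV 20% | CV 30% |
|---|---|---|---|
| One enzyme, P(Week 1 > screening) | 0.36–0.40 | 0.25–0.31 | 0.18–0.25 |
| Same, with a 10% true rise on drug | 0.63–0.66 | 0.38–0.45 | 0.25–0.33 |

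The first row is below one half because people selected for a high first value tend to fall back on the second. If a rise in either ALT or AST counts (true levels correlated at 0.7), the range is about 35–55% with within-person errors also correlated at 0.7, and 61–71% with independent errors. If only an enzyme that was raised at screening counts, it is about 19–46%.

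**6. Counts.** If 5–15% of the 250 enrolled enter this way (assumption), 13 to 38 are retested. Low end: 13 × 0.18 ≈ 2. High end: 38 × 0.55 ≈ 21, or 38 × 0.71 ≈ 27 with independent errors.

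**The case against.** The best case for the plan is that this is safety monitoring of a small group already accepted at screening, and that DSMP section E already lets the investigator withdraw anyone for safety. The missing-data section then deals with the lost outcome by recall, by an all-relapsed run and by comparing missingness by treatment assignment. The rule also does not say what happens after a rise; removal is only its converse. All of this is fair and limits the point. It does not answer it: recall is unverified, counting people as relapsed is not observing them, and a comparison of missingness describes an imbalance without repairing it.

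Several stronger readings are tempting, and the documents do not support them:
- A reader might infer that everyone faces a Week 1 liver test. Only those enrolled with raised values do.
- A reader might see a flat contradiction with the intent-to-treat sentence. That sentence already requires a measured outcome, and its quoted clause concerns taking treatment. The liver rule defeats the stated purpose more than the wording.
- A reader might take the three-month follow-up promise as contradicted. That promise is made regardless of smoking status only.
- A reader might say that the exclusion of liver dysfunction is breached. The term has no threshold, and the operating rules may be meant to define it. The texts need reconciling, but a breach is not shown.
- A reader might assume that the drug raises enzymes. No document says so; the 10% rise above is purely illustrative.

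**Conclusion.** The point holds for the subgroup enrolled with mildly raised ALT/AST. As written, the rule can take randomised participants out of the study on a post-treatment result, 21 days before the primary outcome, and no text keeps them in outcome follow-up. The timing is certain from the documents. Removal after a rise is the natural reading but is not spelled out.

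The size is uncertain. Roughly 2–21 removals (up to 27 with independent errors) rests wholly on assumed variability and an assumed 5–15% entering this way; the true number may be small. The main concern is selection, not power. Bias between arms arises only if enzyme rises differ by arm; without that, the cost is lost participants. The point should be settled, because the remedy is cheap, but it does not by itself undermine the trial.

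**What to change.** In the operating rules and B.4.3, state that a Week 1 liver result does not by itself end outcome follow-up. Participants who consent stay on the existing visit schedule, with TLFB, CO and cotinine at Weeks 4 and 12, and are analysed as randomised. Report anyone removed under this rule by arm, including any already removed.

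Reconcile the operating rules with the exclusion lists in B.4.2 and the DSMP on who is eligible. The medical content of that, and any decision on study drug or safety withdrawal, stays with the study physicians; nothing here prescribes it.

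Cost: a sentence or two of text, and a few participants attending visits that are already scheduled, possibly off drug. No new procedure is needed.

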### **Aim 1: Investigate sex differences in the effect of exogenous PRO compared to placebo on impulsivity and smoking cessation**

Hypothesis 1: For both males and females, a lower proportion of subjects randomized to PRO will relapse by 4 weeks after quit date compared to those randomized to PBO.

Hypothesis 2: For both males and females, subjects randomized to PRO will have more days to relapse compared to those randomized to PBO.

Hypothesis 3: There will be a sex difference in smoking relapse such that females, regardless of randomization assignment, will have fewer days to relapse compared to males.

Hypothesis 4: Impulsivity will be a stronger relapse predictor in females than males.

Hypothesis 5: Among those with higher levels of serum PRO the influence of impulsivity on smoking relapse will be dampened.

Given that less than three percent of those who attempt to quit smoking remain abstinent six months later (Benowitz, 2009), there is an urgent need to gain a better understanding of the dynamic process involved in smoking cessation. This project will provide new knowledge regarding the possible protective role of progesterone against smoking relapse in males and females.

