**Table 1. Timing of Study Procedures by Sex**

	Female Subjects	Male Subjects
Initial Phone Interview		Anytime
Screening Visit 1	Menstrual Cycle Days 1-7	Within 2 weeks of Phone Screen
Screening Visit 2		Within 3 days of Screening Visit 1
Baseline Visit	Within 3 days after LH Surge	Delay matched to Female Subject
Medication Start		8PM on day of Baseline Visit
Quit Date		7 days after Baseline Visit
Week 0		Day of Quit Date
Week 1-Week 11		Weekly
Medication End		Day of Week 11 Visit
Final Visit		12 Weeks after Quit Date

Weeks 0-12 (Visits 4-16): The Week 0 clinic visit will occur on the assigned quit date. Subjects will attend clinic visits on a weekly basis thereafter for twelve weeks. At weeks 0-4, week 8 and week 12 blood samples (hormone measurement) will be collected. Urine samples will be collected at all visits from all participants (pregnancy tests for females; and visual inspection of urine color to confirm compliance with taking study medication via riboflavin filler). At weeks 0-4, week 8 and week 12 urine will be saved for biochemical confirmation of smoking status via nicotine/cotinine levels. Subjects will also complete several forms and questionnaires (described below). Subjects will also return the medication bottle and unused medication, be given a new two-week supply and adverse events will be assessed. At Week 11, study medication will be discontinued. Finally, subjects will receive brief smoking cessation behavioral counseling (Appendix A). At the end of each visit subjects will be paid for their time. These visits will take approximately 30-45 minutes to complete.

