Independent Measures (sex, randomization and serum progesterone): Sex will be collected via self-report on the Demographics form completed at Screening Visit 1. Randomization, assignment (PRO vs. PBO) will be known as of the Baseline Visit to the SAC and Clinical Trials Research Pharmacy, but not will be unblended to other staff or participants until after completion of all measurements. Participants will be informed on their randomization assignment in a letter mailed within six months of the study's completion; this letter will also briefly summarize the study's findings. Measurement of serum progesterone will be measured by collecting a blood sample at clinic visits 0-4, 8 and 12. Blood (20 cc) will be drawn then centrifuged. The serum stored at -20°C in sealed storage tubes to prevent evaporation. Approximately two mL of serum will be analyzed by the HealthEast Medical Laboratories for progesterone sample using chemiluminescence. The remaining serum (approximately two to four mL) will be used for estradiol measurement (described below) and/or stored as back-up to be used in the event that problems occur during analyses.

Other Covariates: Information on potential covariates is collected at the clinic visits, including:

- **Smoking Behavior:** Specifically, number of cigarettes smoked per day during ad libitum smoking, self-reported number of past quit attempts, past longest quit attempt, motivation to quit smoking, and social influences such as partner smoking. This item will be completed at Screening Visit 1 only.
- **Fagerström Test for Nicotine Dependence (FTND; Heatherton et al 1991):** This item will be administered during the first screening session to assess level of nicotine dependence. The FTND is a 6-item self-report measure derived from the Fagerström Tolerance Questionnaire. This item will be completed at Screening Visit 1 only.

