#### B.4.9. Existing Challenges & Barriers

To test our study hypothesis in females, it is critical to produce and maintain serum progesterone levels consistent with those observed in the Luteal phase (6-14 ng/mL; Yee et al, 1999). To do this, we considered many different options for the delivery of exogenous hormones. First, we decided not to use combined synthetic progestin-estradiol hormonal contraceptive pills because this option would further complicate the study design by introducing another variable (exogenous estradiol; Goletiani et al 2007). Second, we also considered using synthetic progestin-only hormonal contraceptive pills. However, as we have observed in our current study, they also do not result in levels of serum progesterone consistent with the Luteal phase. Further, synthetic progestin has more risks associated with it than natural progesterone (Goletiani et al 2007). Next, delivery of progesterone via intravaginal or rectal suppository, or intramuscular injection was eliminated because the serum progesterone levels would still be substantially lower than those typical of Luteal phase. Therefore, using natural micronized progesterone (generic Prometrium) is the best way to ensure serum progesterone levels remain consistent with levels observed during the Luteal phase. Since the half-life of natural progesterone is short, twice daily dosing is necessary. While there may be a question of subject compliance with taking two oral doses per day, we will confirm compliance via the assessment of serum progesterone levels at all study visits postpartum. Natural progesterone is also the easiest way to administer supplemental progesterone for male participants and has been successfully done in other studies (Goletiani et al 2007). On a related note, a second challenge is estrogen. Estrogen fluctuates naturally during the menstrual cycle (Yee et al 1999), and has also been shown to be associated with the facilitation of drug abuse behaviors (Carroll & Anker, 2010). While it is impossible to remove estrogen from our sample population, we will measure it (via blood samples to measure serum estradiol levels) and consider it in our analyses.

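### The rules list sends only one on-treatment hormone sample (Week 4) for assay, and Hypothesis 5 is tested with a pre-dose progesterone value

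*Combined protocol and SAP*

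**What the plan says.** - **Hypothesis.** Hypothesis 5 (Aim 1) reads: "Among those with higher levels of serum PRO the influence of impulsivity on smoking relapse will be dampened". It gives no time point for the serum level.
- **Planned test.** B.4.8 (Other analyses), repeated in section C of the Data Safety and Monitoring Plan (DSMP), tests the interaction of baseline impulsivity with baseline serum progesterone, in logistic models for the binary outcomes and Cox models for days to relapse. Both places say the study is not powered for this and that the results are for generating hypotheses.
- **Collection.** B.4.3 says: "At weeks 0-4, week 8 and week 12 blood samples (hormone measurement) will be collected". B.4.6, which treats serum progesterone as an independent measure, says: "Measurement of serum progesterone will be measured by collecting a blood sample at clinic visits 0-4, 8 and 12". Hormone blood is also taken at the Baseline Visit, and the first dose follows at 8 PM that evening.
- **End of drug.** B.4.3 says: "At Week 11, study medication will be discontinued". The final visit is at Week 12. B.4.9 adds: "Since the half-life of natural progesterone is short, twice daily dosing is necessary".
- **Compliance.** B.4.9 says serum progesterone will confirm compliance at all study visits. (Its wording ties those visits to the postpartum period, which fits nobody in this trial, so I read it as all visits.) B.4.3 also plans inspection of urine colour at all visits and the return of bottles and unused capsules.
- **Assay list.** Under "Samples to be sent for analysis", the Rules/Changes list gives baseline, Week 4 and Week 12 for hormones, and Week 4 and Week 12 for cotinine.

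**The concern.** Serum exposure is the premise of the trial. B.4.5 chose the regimen to reach luteal-phase levels, and B.4.7 bases the expected odds ratios on progesterone differences between arms. If the result is null, the team will need to know whether participants reached those levels during the period of relapse risk. The assay list answers that with one value, taken at the close of the primary outcome window.

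Hypothesis 5 has a related gap. It concerns people with higher serum progesterone, which in this trial should include those given the drug. The planned moderator is measured before anyone takes a capsule, so the test addresses natural progesterone at one point rather than exposure to treatment.

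**Working it through.** **Schedule, with day 0 as the quit date.** Dosing starts on day -7 and lasts twelve weeks (B.4.5): -7 + 84 = day 77, the Week 11 visit. B.4.1 agrees: 7 + 70 + 7 = 84 days. Week 12 is day 84, and 84 - 77 = 7 days after medication ends.

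| Hormone draw | Day | Drug status | On assay list |
|---|---|---|---|
| Baseline | -7 | before first dose | yes |
| Week 0 | 0 | after 7 days of dosing | no |
| Weeks 1, 2, 3 | 7, 14, 21 | on treatment | no |
| Week 4 | 28 | on treatment; primary outcome visit | yes |
| Week 8 | 56 | on treatment | no |
| Week 12 | 84 | 7 days after stopping | yes |

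- Post-baseline draws: 5 + 1 + 1 = 7. On treatment: 6. On treatment and listed for assay: 1 (Week 4).
- Draws after dosing starts and before the Week 4 visit: 4 (Weeks 0-3). Listed for assay: 0.

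**Three schedules for serum progesterone.** B.4.9 implies all 13 weekly visits (Weeks 0-12). B.4.3 and B.4.6 give 7 of them. The Rules/Changes list gives 2, plus baseline.

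**Outcome status when Week 4 blood is drawn.** I use the design rates in B.4.7 and first reproduce its power.
- Placebo relapse is 0.66, so the odds are 0.66/0.34 = 1.941. Dividing by the odds ratio of 3.5 gives 0.555, so progesterone relapse is 0.555/1.555 = 0.357.
- With 50 per arm, two-sided alpha 0.025 and a pooled-variance chi-square test without continuity correction, power is 79.7%. The plan states 80%, so its figure reproduces.
- Relapsed at Week 4 overall: (0.66 + 0.357)/2 = 0.508, or about 102 of 200 completers. For them the only on-treatment value does not precede the outcome. For the other 98 or so, Week 4 blood precedes Week 12 status and any later relapse.

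**People with no Week 4 visit.** They would have no assayed on-treatment value. The plan's figures put them at 250 - 200 = 50, or 0.25 x 250 = about 62. One of the three missing-data analyses in B.4.8 counts them all as relapsed.

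**What the baseline moderator can measure.** It is drawn before the first dose, so randomisation makes it independent of arm apart from chance. B.4.5 expects 0-1 ng/mL in untreated men and 1-14 ng/mL in untreated women depending on phase; women are sampled within three days of the LH surge. If the sexes are pooled, which B.4.8 does not state for this test, the moderator would partly stand in for sex.

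**Effect of swapping Week 12 for Week 0.** Assays per person stay at 3. On-treatment values rise from 1 to 2, and values before the Week 4 visit from 0 to 1. No analysis in B.4.8 or DSMP section C names a Week 12 hormone value.

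**The case against.** A reader might infer three stronger things, and the documents support none of them.

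- **That Hypothesis 5 rests on the Week 4 value and so cannot be tested without reverse causation.** The planned moderator is baseline progesterone, and the assay list keeps baseline. A pre-dose value cannot be caused by later relapse. The weakness is that it does not measure exposure.
- **That compliance rests on one blood value.** Urine colour and returned medication are checked separately. Only the serum check promised in B.4.9 shrinks.
- **That the outcome is always known by Week 4, with relapsers low because they stopped their capsules.** Week 4 blood precedes Week 12 relapse and every relapse after Week 4. Nothing says relapsers stop taking capsules; B.4.3 encourages them to stay and try again.

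It can also be said that the list does not state that it is exhaustive, that its hormone entry is undated, and that it is loosely written: it labels cotinine as blood, where B.4.6 specifies urine. B.4.6 lets remaining serum be "stored as back-up to be used in the event that problems occur during analyses", so later assays may be possible. This stands as a caution. Against it, the cotinine entry names the same two visits as B.4.6 although urine is saved at more, which suggests the list is the intended assay set.

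The objections to Week 0 as a moderator also have force. It is measured after randomisation and mixes assignment with early adherence. In women it falls seven to ten days after ovulation (seven to nine in the DSMP), when the natural luteal range of 6-14 ng/mL overlaps the 9-13 expected on progesterone. A participant may smoke on the quit date itself, and the Rules/Changes list allows a late Week 0 visit as a deviation. These points limit how the added model may be used, and the change below allows for them.

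**Conclusion.** The point holds in limited form. As listed, one of six on-treatment hormone draws is assayed and none before the Week 4 visit, which conflicts with B.4.6 and with the serum check in B.4.9. Separately, the Hypothesis 5 test uses a pre-dose moderator and cannot address exposure to the assigned drug.

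Priority is low. Hypothesis 1 compares randomised arms and needs no on-treatment hormone value, and the plan already treats Hypothesis 5 as preliminary. What is lost is evidence for interpreting a null result and a Hypothesis 5 test that matches its wording.

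This rests on three assumptions: that the list is the complete assay set; that the half-life, which the documents call short without a figure, is short enough for a sample seven days after stopping to say nothing about exposure; and that Week 0 serum is still in storage. The figure of about 102 relapsed at Week 4 applies only at the design rates.

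**What to change.** 1. Reconcile the Rules/Changes list with B.4.6 and B.4.9. State which visits are assayed for progesterone and estradiol, and reword the B.4.9 commitment to match, since three assays would still fall short of every visit.
2. Send stored Week 0 serum in place of Week 12, giving baseline, Week 0 and Week 4.
3. In B.4.8 and DSMP section C, keep the baseline-progesterone model for Hypothesis 5 and add one with Week 0 serum progesterone as moderator, adjusted for sex and treatment arm. Label it exploratory because Week 0 is post-randomisation. Restrict the Cox version to relapses after the Week 0 draw. If the sexes are pooled, carrying the impulsivity-by-sex term from Hypothesis 4 would help stop the interaction from picking up sex.

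Cost: the number of assays is unchanged. The off-drug Week 12 hormone value is lost, though no planned analysis names it. Week 0 should separate the arms in men (6-7 against 0-1 ng/mL expected). In women natural luteal progesterone overlaps with the drug, so Week 0 alone is a weak compliance check, and the urine and returned-medication checks remain necessary.
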